# Methodology:-

**Study design: -** a split-mouth clinical trial.

### Setting & Subjects:

The study will be conducted in a split-mouth design on patients male with missing teeth in the upper or lower jaw (canine to 1st molar area), the subjects will be selected depending on bone density and from those attending to the department of periodontics.

### Inclusion criteria:

1. Patients male have good oral hygiene.

2. Patients were periodontally healthy.

3. Patients had at least two missing teeth in the upper or lower jaw (canine to  $1^{st}$  molar area) indicated for the dental implant.

### **Exclusion criteria:**

1-Patients with any systemic diseases that influence bone healing such as osteoporosis and diabetes mellitus.

2-Fully edentulous.

3-Patients who had parafunctional habits.

4-Smokers.

5-Patients who were not able to follow the treatment protocol.

# Sample Size:

Twenty single-piece endosseous implants use for patients with at least two missing teeth in the upper or lower jaw (canine to 1st molars area).

# Materials:-

1-Melatonin powder (*N*-Acetyl-5-methoxytryptamine) from (Sigma-Aldrich/Germany).

2-Periotest M device (Medizintechnik Gulden, Germany).

3-Dentium implant surgical kit system and DI fixtures (Dentium Co., Korea).

# **Procedure:**

Twenty single-piece endosseous implants (Dentium Co, Korea) will use to restore missing teeth in the upper or lower jaw (canine to 1st molars area) from both sides. The study will be split-mouth technique, each patient serves as his own control (served into 2 groups), the study side (topical application of melatonin in the implant side), and the control side (no melatonin in the other implant side of the same patients). According to the study reported by **(Cutando et al., 2008)** the estimated dose of melatonin required to enhance osseointegration of dental implant and minimize the marginal bone resorption is 1.2 mg of melatonin powder for each implant. CBCT for all patients before implant placement to determine bone density, dimension, and anatomical landmarks. Prior to surgery, all patients will instruct to use chlorhexidine 0.12% mouthwash as antiseptic. After local anesthesia, a mucoperiosteal flap will reflect. The manufacturer's instructions should be followed for the preparation of the implant osteotomy site. For the study

side, 1.2 mg of melatonin powder will place in the osteotomy site before the insertion of the implant. For the control side, no melatonin powder will be used and implants will be inserted directly in the prepared implant site. After dental implant installation, the gingival former will insert into the body of the fixture, then the Periotest M device will use to measure the primary stability of the DI fixture. After that, the gingival former will be removed and cover screw place and tightened into the fixture. Sutures will place after flap replacement. Patients should be instructed to use antibiotics amoxicillin 500mg and metronidazole 500mg 3 times/day for 5 days after surgical procedure, soft diet and proper oral hygiene measures. Also, CBCT immediately after implant placement to record baseline bone level, CBCT after 6 months follow up to measure marginal bone level around implant comparing with baseline measurement, and measure the secondary stability using periotest M device.

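### The protocol gives no random or other rule for which site in each mouth receives melatonin, so a side difference could reflect how the sites were chosen

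*Protocol*

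**What the plan says.** Under Methodology, the study design is given as "a split-mouth clinical trial" and nothing more. The Procedure section says "each patient serves as his own control (served into 2 groups"), and then identifies "the study side (topical application of melatonin in the implant side), and the control side (no melatonin in the other implant side". It sets no rule for choosing between the two.

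Other statements bear on the point:

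- **Site information before surgery (Procedure):** "CBCT for all patients before implant placement to determine bone density, dimension, and anatomical landmarks".
- **Control treatment (Procedure):** "For the control side, no melatonin powder will be used and implants will be inserted directly in the prepared implant site".
- **Eligible sites (Inclusion criteria):** "Patients had at least two missing teeth in the upper or lower jaw", in the canine to first molar area. The Procedure adds that implants are placed on both sides.
- **Patient selection (Setting & Subjects):** "the subjects will be selected depending on bone density".
- **Bone outcome (Procedure):** "CBCT after 6 months follow up to measure marginal bone level around implant comparing with baseline measurement".

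The Sample Size section gives 20 implants and no number of patients.

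**The concern.** The Research Hypothesis is causal: melatonin is said to affect osseointegration and to reduce marginal bone loss. The comparison of the two sides is the only evidence the trial will produce for it. A split-mouth design supports a causal reading when chance decides which site is treated. Here the methods leave that open, and the person choosing may already know the bone density and dimensions of both sites.

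Site quality could plausibly affect both implant stability and later bone loss. If melatonin tends to go to the better site, the result is flattered. If it tends to go to the poorer site, a real benefit may be hidden. Readers of the eventual report could not tell which of these happened, if either.

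**Working it through.** **Search for a rule.** The methods, from the aim to the stopping rules, contain no randomisation, coin toss, alternation, fixed left/right convention, matching of sites, concealment or named person who decides. Random allocation is mentioned only where the introduction and the reference list describe other studies.

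**What pairing does and does not remove.** For each patient,

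observed side difference = melatonin effect + (quality of melatonin site − quality of control site) × its influence on the outcome + noise.

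Patient-level factors cancel. The site term averages to zero only if the choice of side is unrelated to site quality. Otherwise it stays in the estimate, and a larger sample does not shrink it.

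**Do other features of the plan close the gap?**

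- Selecting patients on bone density may narrow the range, but it does not match the two sites within a patient.
- Comparing the 6-month bone level with the same implant's baseline removes a difference in starting level. It does not remove a density-driven difference in later loss.
- The first Periotest reading is taken after the implant, and on the study side the melatonin, is in place. It can show an imbalance but cannot prevent one.

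**Illustration of size.** The Protocol gives no figure to reproduce here. Every input below is an assumption.

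- One outcome difference per patient, scaled to SD 1. For marginal bone level this is the change from baseline.
- Correlation r between site-quality difference and outcome difference: 0.3, 0.5 or 0.7.
- Melatonin goes to the better site with probability p.
- Paired t-test, two-sided 5%; 200,000 simulated trials per case.
- 10 pairs, which is 20 implants ÷ 2 if each patient has exactly one pair.

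The bias in SD units is (2p − 1) × √(2/π) × r, with √(2/π) = 0.798. For p = 0.8 and r = 0.7 this is 0.6 × 0.798 × 0.7 = 0.34.

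With no true effect and 10 pairs, for r = 0.3 / 0.5 / 0.7:

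| Choice of side | Bias (SD) | False significance favouring melatonin |
|---|---|---|
| Random, p = 0.5 | 0 | 2.5% throughout |
| Better site in 65% | 0.07 / 0.12 / 0.17 | 4% / 5% / 7% |
| Better site in 80% | 0.14 / 0.24 / 0.34 | 6% / 11% / 18% |
| Poorer site in 80% | −0.14 / −0.24 / −0.34 | under 1% (against melatonin: 6% / 11% / 18%) |

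With a true effect of 1.0 SD and 10 pairs, power is 80% under random choice. It falls to 68% / 60% / 52% when the poorer site is chosen in 80% of patients.

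With 5 patients, one difference each, the 80% better-site case gives 4% / 7% / 10% false significance with the same bias.

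**The case against.** **No biased choice is described.** The document gives CBCT a planning purpose and nowhere says that site quality decides the side. That is correct. What is shown is an unstated rule, not a biased one, and the bias may be nil. But the plan as written permits a choice made with the scans in hand, and nothing in it would reveal that.

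**Eligibility is narrower than any two gaps.** The Procedure has implants on both sides, within a span from canine to first molar. This narrows the possible mismatch, but it requires neither the same tooth position nor equal bone density.

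**The simulation inputs are invented.** This also stands. At the mild end, false significance moves only from 2.5% to 4%, and the 18% needs both strong preference and a high correlation. The figures show scale and are not evidence that bias will occur.

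**The rule may be elsewhere.** The title and front pages were not available, and a rule there cannot be excluded. The word randomised in a title alone would still supply neither a method nor concealment. A separate analysis plan is no answer, because allocation is fixed at surgery and belongs in the protocol.

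**Blinding is a different matter.** The absence of powder on the control side means the operator knows the assignment at surgery. It says nothing about how the side was chosen, and the point does not rest on it.

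**Conclusion.** The concern holds. The methods name a melatonin side and a control side and give no rule for assigning them, while site quality is visible beforehand and the sites need not match. The trial's only causal comparison is therefore open to a site effect that pairing does not remove and later analysis cannot reliably repair.

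This conclusion rests on the text and needs no number. The size and direction of any bias are unknown: it is zero if the choice is unrelated to site quality, and about 0.07 to 0.34 SD of the within-patient difference, in either direction, under the preferences assumed above. It should be corrected before the first implant is placed.

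**What to change.** In Study design and Procedure, state that melatonin is assigned at random to one of the two sites within each patient, and describe the trial as a randomised split-mouth trial. Specify:

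- a list prepared in advance by someone who does not operate, sized to the actual number of patients and implant pairs;
- concealment, for example in sealed opaque envelopes;
- opening only after both sites are confirmed eligible and, where both are operated on in one session, after both osteotomies are prepared;
- preferably no fixed total per side, since that makes the last allocations predictable in so small a trial. Left/right balancing is defensible if the list stays concealed.

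Record tooth position and pre-operative bone density for each site, so that the balance achieved can be shown.

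The cost is one or two sentences, a set of envelopes and one list, with no extra patients or visits. If implants have already been placed without random assignment, the protocol should state the rule actually used and soften the causal wording of the hypothesis.

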resorption(Cutando et al., 2008, Witt-Enderby et al., 2006). In addition to this, in vitro research has reported that melatonin can increase osteoblast proliferation and differentiation (López-Martínez et al., 2012, Muñoz et al., 2012). So was proposed that the local application of melatonin during surgical implant placement procedures would be an effective treatment technique for dental implant osseointegration (Dundar et al., 2016). Worthy osseointegration is a prerequisite for dental implants. Optimal osseointegration depends on the formation of new bone around implants, which may be stimulated by the application of biomimetic agents (Ramazanoglu et al., 2011). Considering the bone metabolism, melatonin acts directly on the osteoclast, a multinucleated cell, which resorbs the extracellular matrix through various mechanisms, including the production of free radicals (Roth et al., 1999). Moreover, in pre-osteoblast cultures from rats, melatonin, in a dose-dependent manner, promoted the development of bone sialoprotein and other protein bone markers, including alkaline phosphatase, osteopontin, and osteocalcin, and speeds up their period of differentiation into osteoblasts from the normal rate, which is 21 days, to 12 days, this reaction is mediated by the membrane receptors for the indole(Roth et al., 1999). Also, melatonin, may interfere with the function of the osteoclast and thereby inhibit bone resorption(Cardinali et al., 2003). (Cutando et al., 2008) conducted an experimental study using melatonin with dental implants in dogs. Two weeks after implant insertion, melatonin significantly increased all parameters of osteointegration. It has been observed that melatonin, increases bone mass by suppressing resorption through down-regulation of the RANKLmediated osteoclast formation and activation (Cutando et al., 2007). These data point towards an osteogenic effect of melatonin that may be of clinical importance, as it could be used as a therapeutic agent in situations in which bone formation would be advantageous, such as in the treatment of fractures or of osteoporosis (Cardinali et al., 2003).

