### **Objectives:** -

1- Measuring primary and secondary stability of the dental implant by Periotest M device.

2- Measuring marginal bone level around the dental implant in baseline and after 6 months follow up using a cone-beam computed tomography (CBCT).

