# Null hypothesis:-

The topical application of melatonin powder in the osteotomy site has no effect on osseointegration around the dental implants and in minimizing marginal bone loss.

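### Does the protocol judge melatonin by before-after change within an implant, and treat primary stability as an outcome, instead of comparing the two sides?

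*Protocol*

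**What the plan says.** The Procedure fixes the design: "The study will be split-mouth technique, each patient serves as his own control (served into 2 groups". One side receives melatonin, and the comparator is "the control side (no melatonin in the other implant side of the same patients". The Null hypothesis is that topical melatonin "has no effect on osseointegration around the dental implants and in minimizing marginal bone loss". The Research Hypothesis is the corresponding positive statement.

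The two Objectives list what is measured. The first is "Measuring primary and secondary stability of the dental implant by Periotest M device". The second is "Measuring marginal bone level around the dental implant in baseline and after 6 months follow up using a cone-beam computed tomography (CBCT". Neither names a test or a contrast.

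The Procedure then gives the sequence of measurements. After the implant is placed, "then the Periotest M device will use to measure the primary stability of the DI fixture". A CBCT immediately after placement records the baseline bone level. At 6 months the scan is repeated, "CBCT after 6 months follow up to measure marginal bone level around implant comparing with baseline measurement", and secondary stability is measured.

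**The concern.** Read alone, the 6-month sentence compares an implant with itself over time. Bone around an implant changes on both sides whether or not melatonin works, so such a comparison shows healing and not a treatment effect. In a small trial it also invites a familiar error: finding significance on the treated side and none on the control side, and reading that as a treatment effect.

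Objective 1 raises a second doubt. It puts primary and secondary stability in one line under an aim of evaluating osseointegration. The mechanism described in the Introduction takes days; in rat cell cultures melatonin "speeds up their period of differentiation into osteoblasts from the normal rate, which is 21 days, to 12 days". A reading taken straight after insertion cannot show that. If primary stability were tested as an outcome, it would add a comparison that cannot answer the question. With three independent tests at 5% the chance of at least one false positive is 1 − 0.95³ = 14.3%, against 1 − 0.95² = 9.75% with two.

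**Working it through.** The protocol gives no figure to reproduce here: no alpha, power, effect size, SD or correlation. The question is one of reading. The arithmetic only shows what each reading would imply.

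**Reading the text**

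1. *Which contrast is intended?* The Null hypothesis is about melatonin. A before-after comparison on one side cannot test it, whereas a comparison of the two sides can, and the Procedure supplies those two sides within each patient.
2. *What does the 6-month sentence do?* It stands in a list of measurement steps. Marginal bone loss is by definition a change in level from a starting scan, so comparison with baseline is how one value per implant is obtained. That value is then available for the side-to-side comparison. No sentence says each side will be tested against its own baseline.
3. *Is primary stability an outcome?* Objective 1 says only that it is measured. Objective 2 lists the baseline bone level beside the 6-month level in just the same way, and nobody would take that baseline for an outcome. Using the primary reading as the starting value is fully consistent with Objective 1.

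**What the two analyses would do**

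Assumptions, none given in the protocol: 10 patients with one implant per side (Sample Size states only 20 implants), two-sided 5% tests, normal data, the same true change on both sides, at least 100,000 simulated trials per setting. Let *a* and *b* be the changes on the melatonin and control sides, in SD units of change.

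- Separate tests: *t* = mean(*a*) / (SD(*a*)/√10), and likewise for *b*.
- Paired test: *t* = mean(*a* − *b*) / (SD(*a* − *b*)/√10).

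| True change, both sides (SD) | Melatonin side alone significant, correlation 0 | Same, correlation 0.5 | Same, correlation 0.7 | Paired test |
|---|---|---|---|---|
| 0.5 | 21% | 15% | 12% | 5% |
| 0.65 | 25% | 18% | 14% | 5% |
| 0.9 | 20% | 15% | 11% | 5% |
| 1.0 | 16% | 12% | 9% | 5% |
| 1.2 | 8% | 6% | 5% | 5% |
| 1.5 | 1% | 1% | 1% | 5% |

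The 15% to 25% range belongs to changes of 0.5 to 0.9 SD with correlation 0 to 0.5, which brackets the worst region. It falls away outside it. The paired test holds 5% throughout.

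**Is adjustment for baseline needed for a sound result?**

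Take the side difference at 6 months with SD 1, and let *r* be its correlation with the side difference at baseline. Three paired analyses are valid: difference in change, difference in 6-month values, and the 6-month difference adjusted for the baseline difference (8 residual degrees of freedom instead of 9). Mean width of the 95% confidence interval with 10 pairs:

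| *r* | Change | 6-month only | Adjusted | Adjusted vs change | Adjusted vs 6-month only |
|---|---|---|---|---|---|
| 0 | 1.969 | 1.392 | 1.506 | 24% narrower | 8% wider |
| 0.3 | 1.645 | 1.391 | 1.434 | 13% narrower | 3% wider |
| 0.5 | 1.391 | 1.392 | 1.303 | 6% narrower | 6% narrower |
| 0.7 | 1.077 | 1.391 | 1.073 | equal | 23% narrower |
| 0.8 | 0.880 | 1.391 | 0.903 | 3% wider | 35% narrower |
| 0.9 | 0.622 | 1.391 | 0.656 | 5% wider | 53% narrower |

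No choice is best everywhere. Adjustment is a sensible default, but the protocol commits to none of the three, so it fixes nothing badly. For stability there is a further point: the Procedure places the powder before the implant and takes the primary reading afterwards. That reading is thus not strictly a pre-treatment value, and adjusting for it would remove any immediate mechanical effect of the powder.

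**The case for a change.** The strongest case for the concern is that a protocol should turn its hypothesis into a stated comparison. This one writes out a single comparison, within an implant, and leaves the side-to-side difference to be inferred. The error it might invite is real and common, and a sentence to prevent it would cost nothing. Primary stability is also left without a label, although it cannot reflect new bone.

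The observations stand. The melatonin-minus-control difference is nowhere written as a formula, and the primary reading is called neither baseline nor outcome. The inference drawn from them does not stand. An implicit contrast is not a wrong one when the design and both hypotheses allow only one reading, and an unlabelled measurement is not one wrongly declared an outcome. The exact contrast, the covariate and the order of testing are ordinarily set in a statistical analysis plan. None is at hand for this trial, so their absence from the protocol cannot be counted against it.

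**Conclusion.** The concern does not hold. The protocol's contrast is melatonin side against untreated side within a patient. The comparison with baseline defines bone loss for each implant, and primary stability is listed only as something measured. Anyone who follows the split-mouth design with a paired comparison of 6-month change or of secondary stability gets a test with a type I error of about 5%. The false-claim rate of 15% to 25%, and the 14.3% for three tests, describe analyses that the protocol does not state.

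The reading rests on the text alone. The simulated figures rest on 10 pairs, normal data, two-sided 5% tests, and sides that are comparable when melatonin has no effect; how the sides are allocated is a separate matter. The conclusion would change if a statistical analysis plan specified separate before-after tests on each side as the evidence for melatonin, or a test of primary stability as evidence of osseointegration.

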# **Research Hypothesis:-**

The topical application of melatonin powder in the osteotomy site has an effect on osseointegration around the dental implant and minimize marginal bone loss.

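### The protocol does not keep the treated side from whoever takes the Periotest readings or measures the CBCT images, so expectation-related reading bias between sides is uncontrolled

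*Protocol*

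**What the plan says.** The Procedure section describes an open intervention. On the study side, "1.2 mg of melatonin powder will place in the osteotomy site before the insertion of the implant". On the other, "For the control side, no melatonin powder will be used and implants will be inserted directly in the prepared implant site".

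The same section then orders four readings per implant. A Periotest reading of primary stability is taken during the operation, after installation. Next comes "CBCT immediately after implant placement to record baseline bone level". At follow-up there is "CBCT after 6 months follow up to measure marginal bone level around implant comparing with baseline measurement", followed by "and measure the secondary stability using periotest M device".

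These readings are the whole of the Objectives section: "Measuring primary and secondary stability of the dental implant by Periotest M device" and "Measuring marginal bone level around the dental implant in baseline and after 6 months follow up". The Research Hypothesis says that melatonin "has an effect on osseointegration around the dental implant and minimize marginal bone loss", and the dose rationale in the Procedure section speaks of enhanced osseointegration. The expected better side is therefore stated.

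None of the sections available names the person who takes the Periotest readings or measures the CBCT images, or says that this person is unaware of the treated side.

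**The concern.** In a split-mouth trial the comparison is between two sides of one mouth. Pairing removes differences between patients. It does nothing about an assessor who knows which side was treated and which result is hoped for. If that knowledge shifts a reading, even slightly and unintentionally, the shift falls on the between-side difference that the trial is meant to estimate. Both objectives depend on such readings, so no outcome in the protocol is outside the concern.

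Who reads an outcome, and what that person knows, is a matter of trial conduct fixed when the value is recorded. It is not something a protocol would normally leave to a statistical analysis plan.

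**Working it through.** The protocol gives no figure on this point to reproduce. The check is a comparison of its sections, plus a short piece of algebra that shapes the fix.

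**1. Is any masking described?** The study design line calls the trial split-mouth and adds nothing on masking. Double-blinding appears only for cited studies, in the toxicology section and the reference list. None of it refers to this trial.

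**2. What does each reading look like?**

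| Reading | Assessor named | Side concealed | Masked reading possible later |
|---|---|---|---|
| Periotest at surgery | No | No; taken just after the powder is placed | No |
| CBCT after placement | No | Not stated | Yes, from stored images |
| CBCT at 6 months | No | Not stated | Yes, from stored images |
| Periotest at follow-up | No | Not stated | No, live reading |

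**3. Can the person reading affect the value?** For Periotest, the device section points both ways. It describes a digital display, calls the wireless model simpler for objective evaluation, and reports good repeatability, although that evidence is introduced for the classic wired model. It also lists rod position and angle as possible influences on the value. For CBCT, marginal bone level has to be measured on an image, and no masked reading is described. Some scope for influence exists. Nothing ties it to knowledge of side.

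**4. What survives in the comparison?** Let b0 and b6 be the reading shift in the between-side difference at baseline and at six months.

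- Six-month values compared: bias = b6.
- Change from baseline compared: bias = b6 − b0.

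Analysing change therefore cancels only a shift that is equal at both times. This matters for the remedy. Suppose both Periotest readings are open with equal shifts of 0.5 SD of the analysed difference. The change score carries 0.5 − 0.5 = 0. If only the six-month reading is masked, so that b6 = 0, the change score carries 0 − 0.5 = −0.5, a bias of opposite sign. The six-month comparison then carries 0.

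To show what that can mean, assume 10 independent pairs (20 implants, one per side), no true effect and a two-sided 5% paired t-test. The noncentrality is 0.5 × √10 = 1.58 on 9 degrees of freedom, and the rejection probability is about 29% instead of 5%. The 0.5 SD, the 10 pairs and the test are all assumptions. The figure explains why the Periotest fix needs a second comparison; it is not evidence of how large the problem is in this trial.

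**The case against.** The strongest reply is that this rests on silence. No sentence in the protocol is wrong, none says that the surgeon or an unmasked person reads the outcomes, and the title and similar pages were not available for checking. That limits the claim: masking is not described, which is different from showing that it will not happen. It does not remove the claim, because the Procedure section sets out each measurement step by step and omits the safeguard.

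Second, Periotest gives a digital value, and the link from rod angle to expectation is an inference. This stands. A repeatable instrument can still be held differently on two sides, but the protocol does not show that it would be.

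Third, a later document could require masked measurement of the CBCT images, since they are stored. This also stands. Only for the live Periotest readings is it true that a later plan cannot remove the bias.

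Fourth, masking Periotest at six months alone may leave a change score worse off than leaving both readings open, and taking the side out of the chart does not mask a surgeon who remembers it. Both points are correct and are reflected in the fix.

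A reader might also infer that a sham powder is required. Masking the assessor does not need one, and the protocol describes no mark at six months that would reveal the treated side.

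**Conclusion.** The concern holds as an uncontrolled risk. The treated side is open at surgery, both objectives rest on readings taken or measured afterwards, and no available section conceals the side from the person responsible. It is worth correcting before readings begin, mainly because the correction is cheap.

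Its size is unknown. The protocol gives no SD, correlation, test or number of patients, so no shift can be expressed in Periotest units or millimetres, and no false-positive rate can be attached to this trial.

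A reader might infer that the results will favour melatonin, that the surgeon is the assessor, or that the data would be beyond repair. The documents support none of these. They are silent on the assessor, they show neither the presence nor the direction of bias, and the CBCT part can still be read masked from stored images.

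**What to change.** Add a paragraph to the Procedure section.

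**CBCT.** Crop the baseline and six-month images per implant, code them at random, and have them measured in random order without the treated-side record. The reader should be an existing team member other than the operating surgeon where one is available. Break the code only after the measurements are locked.

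**Periotest.** State who takes each reading. Keep the side record from the six-month assessor. Report the surgical reading as unmasked. Present the six-month between-side comparison alongside any change score, because a shift in the open surgical reading would otherwise pass into the change.

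**Cost.** One paragraph and some image-coding time; no extra visit or scan. The protocol describes a self-funded postgraduate thesis and does not show that a second reader exists. If the surgeon has to be the reader, masking is only partial, since with about 20 implants a site may be recognised even on coded images. The report should then say so.
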